### 6.3 Safety Analysis Set

The safety analysis set consists of all subjects randomized and received at least one dose of investigational product. This analysis set will be used for the analyses of all safety endpoints.

### 6.4 Sialic Acid (SA) Analysis Set

The SA analysis set will consist of all randomized subjects with evaluable free serum SA levels at any time point.

## 7 DATA SCREENING AND ACCEPTANCE

### 7.1 Handling of Missing and Incomplete Data

Missing clinical outcome data can occur for multiple reasons, including missed patient visits and scales or measures with missing item scores. Missing and incomplete data will be identified through a review of tables and listings for this study. Missing and incomplete data will be identified for investigation, and possible resolution, by Data Management prior to the study database lock.

Missing measurements in HHD individual muscle group test will be imputed as 0 if the reason for missing is due to weakness. When the measurement for one side is missing, the measurement from the other side will be used to impute the missing value. For UEC and LEC, if measurements are missing for both sides while patients are still in study, the composite score will not be computed. Such cases are expected to be limited. Details of missing observation handling in HHD for individual muscle group are provided in [Appendix 10.2](#). The handling of missing data in individual questions in GNEM-FAS can also be found in [Appendix 10.2](#).

In general, randomly missing assessments for an individual subject would remain as missing. The important case for imputation will be those subjects who are in the study for some period of time but decline in function and leave the study, regardless of whether this decline is the reason listed for withdrawal. The GEE method might not adequately cover the projected decline for these subjects and may not be appropriately conservative. In such cases a single imputation method will be used to estimate the change in strength over the remaining time of the study and these imputed values will be used for the GEE analysis.

For those early-withdraw subjects who are in the study for some period of time (defined as at least one non- missing post-baseline visit) but decline (defined as negative change from baseline to the last non-missing post-baseline visit), all missing post-baseline data will be imputed for the HHD efficacy endpoints such as UE, LE, and Knee extensors. The imputed values are calculated using the subject's average change at previous time points adjusted by the timing of missing data. For example, for a subject with only the first 2 data values the average of the existing values is taken and the rest are imputed by multiplying the average by the (duration of each missing)/(duration of last non missing). See [Table 7.1.1](#) for an upper extremity example.

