**Table 7.1.1: An example of the imputation method for a subject with only 2 values**

Week	Change from baseline	Average of existing data	Imputed values
8	-1		
16	-2		
		-1.5	
24	Missing		$-1.5 \times (24/16) = -2.25$
32	Missing		$-1.5 \times (32/16) = -3.00$
40	Missing		$-1.5 \times (40/16) = -3.75$
48	Missing		$-1.5 \times (48/16) = -4.50$

In order to avoid extreme cases of imputed values that would not reflect the clinical course of the disease, if any of the imputed values for a subject obtained using the proposed method yields values greater (in magnitude) than the worst observed decline of all other subjects at the imputed time point, then the worst observed decline of the other subjects at that time point will be used. This will be done separately for each treatment group.

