## 8 STATISTICAL METHODS OF ANALYSIS

### 8.1 General Principles

Efficacy analyses will be based on the primary analysis set. GEE analysis ([Hanley et al. 2003](#)) for repeated measures will be performed to compare the two treatment groups with respect to the changes from baseline of primary endpoint, secondary endpoints, and all tertiary efficacy endpoints, using an exchangeable working covariance structure among time points. Baseline, gender and region will be included as covariates in the model. Compound symmetry may be used if convergence is not achieved or if the AIC is larger than the one from the exchangeable covariance structure.

In general, randomly missing efficacy data for an individual subject will be treated as missing. The GEE method might not adequately cover the projected decline for these subjects and may not be appropriately conservative. In such cases a single imputation method will be used to estimate the change in strength over the remaining time of the study as described in [Section 7.1](#) and these imputed values will be used for the GEE analysis. This method of imputation will be the primary analysis method for all repeated measures endpoints.

A sensitivity analysis without use of the single imputation method for dropouts will be also be performed using the same GEE model.

The statistical analyses will be reported using summary tables, figures, and data listings. Statistical tests will be 2-sided at the alpha =0.05 significance level. All analyses and tabulations will be performed using SAS®. Continuous variables will be summarized with means, standard deviations, standard errors, medians, minimums, and maximums. Categorical variables will be summarized by counts and by percentages of subjects in corresponding categories.

The final analysis will be conducted at Week 48.

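### SAP 7.1 can impute a growing strength gain to a dropout whom it classes as declining, and its cap does not prevent this

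*SAP*

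**What the plan says.** SAP 7.1 imputes for subjects who withdraw early, have at least one post-baseline value and show "decline (defined as negative change from baseline to the last non-missing post-baseline visit". For them, "all missing post-baseline data will be imputed for the HHD efficacy endpoints such as UE, LE, and Knee extensors". The imputed value is the mean of the subject's observed changes, scaled by time: "the rest are imputed by multiplying the average by the (duration of each missing)/(duration of last non missing". Table 7.1.1 gives one worked case, titled "An example of the imputation method for a subject with only 2 values".

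The only bound follows that table. If an imputed value "yields values greater (in magnitude) than the worst observed decline of all other subjects at the imputed time point", that worst decline replaces it, separately in each arm.

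The reason given for imputing is that "The GEE method might not adequately cover the projected decline for these subjects and may not be appropriately conservative". SAP 8.1 makes the imputed data the basis of the primary analysis, and SAP 8.7 reads the treatment comparison from the Week 48 least-squares means. SAP 8.1 also plans a check: "A sensitivity analysis without use of the single imputation method for dropouts will be also be performed using the same GEE model".

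**The concern.** The test for decline uses one quantity (the last change) and the projection uses another (the mean change). Nothing requires the mean to be negative, or to be as low as the last measurement. Two results follow.

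- If the last change is negative but the mean is positive, the subject qualifies as a decliner and is then given a gain that grows with every missing visit.
- If the mean is much smaller in size than the last change, the imputed value shows less decline than the subject had already lost.

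Both run against the reason for imputing, and both enter the primary model. The cap adds an ambiguity, because it compares magnitudes without saying whether gains count. Two programmers could build different primary datasets from the same text. The one worked example shows neither problem, so it would not bring them to light.

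**Working it through.** **Rule.** Imputed change at week w = (mean of observed changes) × w / L, where L is the week of the last observed value. Visits are at Weeks 8, 16, 24, 32, 40 and 48.

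**Reproducing Table 7.1.1.** Changes -1 and -2, mean -1.5, L = 16. Week 24: -1.5 × 24/16 = -2.25. Week 32: -3.00. Week 40: -3.75. Week 48: -4.50. All four match the SAP.

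**Growing gain.** Changes +3, +2, -0.5 at Weeks 8, 16 and 24. The last change is below 0, so the subject is classed as declining. Mean = 4.5/3 = +1.5, L = 24.

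- Week 32: 1.5 × 32/24 = +2.0
- Week 40: 1.5 × 40/24 = +2.5
- Week 48: 1.5 × 48/24 = +3.0

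This needs at least two observed values. With one, the mean equals the last change and is negative.

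**The cap in this case.** Suppose the worst Week 48 decline among the others in the arm is -2.5 (assumed). Read literally, +3.0 exceeds 2.5 in magnitude and becomes -2.5. Read as covering declines only, it stays at +3.0. If the worst decline is larger than 3.0 in size, the gain stands on either reading.

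**Less decline than measured.** For a steady -1 kg per visit over k visits, the mean is -(k+1)/2 and L = 8k, so Week 48 = -(k+1)/2 × 48/(8k) = -3(k+1)/k.

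| Last visit | Measured there | Imputed Week 48 |
|---|---|---|
| Week 8 | -1 | -6.00 |
| Week 16 | -2 | -4.50 |
| Week 24 | -3 | -4.00 |
| Week 32 | -4 | -3.75 |
| Week 40 | -5 | -3.60 |

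The last two rows show less loss than was already recorded, although the decline is perfectly regular.

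**How often (assumed inputs).** Linear decline averaging -3 kg over 48 weeks, slope SD 4, visit SD 2, dropout unrelated to outcome, cap not applied. About 8% to 14% of imputed decliners receive a gain. For last visits at Weeks 16, 24, 32 and 40, the shares imputed better at Week 48 than their last value are 25%, 41%, 62% and 79%. In a second assumed setting (drug 0, placebo -5 kg at Week 48, same SDs), imputed gains number about 0.23, 0.47 and 0.94 of 80 subjects at 5%, 10% and 20% dropout.

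**Size for one subject.** Setting the example's Week 48 value to 0 in place of +3.0 moves the mean of an arm of 40 by 3.0/40 = 0.075 kg, if the least-squares mean follows one-for-one. The design standard error is 6 × √(2/40) = 1.34 kg, so this is 0.075/1.34 = 0.06 of it.

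**Comparing two repairs (same SDs, error against the true Week 48 change).** Barring gains changes the root mean square error by about -0.18 to +0.02 kg across linear decline and a plateau from Week 24. Holding values at or below the last observed change gives a mixed result for Week 40 leavers: 2.45 to 1.94 kg (better) under linear decline, but 1.09 to 1.72 kg (worse) under the plateau.

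**The case against.** The strongest reply is that little turns on this. No dropout rate is stated. Protocol 5.2.3 reports 47 Phase 2 subjects, of whom 46 entered the extension. If 1/47, about 2%, is taken as a rough proxy for dropout, about 0.1 of 80 subjects would be imputed a gain. The planned analysis without imputation already shows the rule's whole effect. Under SAP 8.2, an early-termination visit on Day 310 or later counts as an observed Week 48, so some Week 40 leavers need no imputation. All of this stands on size. None of it mends the primary rule: the sensitivity analysis removes the rule and does not correct it.

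It can also be said that averaging noisy dynamometry values is defensible, and that the natural reading of the cap is declines only. The first is fair, and is why the divisor and the mean can stay. The second is probably what was meant, which is a reason to write it down.

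Three stronger readings are tempting, and the documents do not support them.

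- That the rule biases the trial toward the drug. The direction depends on which arm loses more decliners, and the documents do not say.
- That every imputed value should be held at or below the last observed change in the primary analysis. Subjects enter the rule because their last value is negative, so anchoring there builds in regression to the mean. It also overstates loss for late leavers if decline plateaus. Protocol 7.2 says that Phase 2 results at 48 weeks resembled those at 24 weeks, so a plateau is not excluded.
- That the rule reaches every endpoint, because SAP 8.1 says "This method of imputation will be the primary analysis method for all repeated measures endpoints". The same paragraph speaks of change in strength and refers back to 7.1, which names the dynamometry endpoints, and SAP 8.8.4 excludes imputation for the laboratory outcomes.

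**Conclusion.** The point holds as a minor one. The algebra is certain: the formula that reproduces Table 7.1.1 also gives rising gains to a subject classed as declining, and less decline than was measured to some late leavers. The first contradicts the stated aim outright, and the cap neither prevents it nor is clear about it. The second is a trade-off between two imperfect projections and does not justify replacing the primary rule.

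The effect on the Week 48 contrast is expected to be small, about 0.06 of the design standard error for one affected subject such as the example. The frequencies and errors in kg are illustrative. They assume normal slopes and visit noise, with dropout independent of decline. The assumed SDs give a Week 48 SD of √(4² + 2²) = 4.5 kg, against the 6 kg in SAP 3.7, and they leave out the early-termination mapping.

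**What to change.** Before unblinding, add to SAP 7.1: *No imputed change for a subject classed as declining may be greater than 0; a positive imputed value is set to 0. The cap applies to imputed declines only.* The example subject is then imputed 0 at Weeks 32, 40 and 48. Table 7.1.1 is unchanged, since all its imputed values are negative.

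Add one sensitivity analysis in which, at visits after the last observed visit, no imputed change is better than the last observed change, subject to the existing cap. There the example subject is held at -0.5, and the two late leavers above at -4 and -5 at Week 48, unless the cap applies. Keep this out of the primary analysis, and keep the planned analysis without imputation.

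The cost is two sentences, a line of code and one extra table. Imputed values shift very slightly toward decline. The bound also acts at a visit missed before the last observed one: with +3, missing, -1, the Week 16 value goes from 1 × 16/24 = +0.67 to 0.

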**Table 7.1.1: An example of the imputation method for a subject with only 2 values**

Week	Change from baseline	Average of existing data	Imputed values
8	-1		
16	-2		
		-1.5	
24	Missing		$-1.5 \times (24/16) = -2.25$
32	Missing		$-1.5 \times (32/16) = -3.00$
40	Missing		$-1.5 \times (40/16) = -3.75$
48	Missing		$-1.5 \times (48/16) = -4.50$

In order to avoid extreme cases of imputed values that would not reflect the clinical course of the disease, if any of the imputed values for a subject obtained using the proposed method yields values greater (in magnitude) than the worst observed decline of all other subjects at the imputed time point, then the worst observed decline of the other subjects at that time point will be used. This will be done separately for each treatment group.

## 7.2 Partial or Missing Dates Imputation Rules

The following conventions will be used to impute missing portions of dates for adverse events and concomitant medications. Note that the imputed values outlined here may not always provide the most conservative date. In those circumstances, the imputed value may be replaced by a date that will lead to a more conservative analysis.

### A. Start Dates

- 1) If the year is unknown, then the date will not be imputed and will be assigned a missing value.
- 2) If the month is unknown, then:
  - i) If the year matches the first dose date year, then impute the month and day of the first dose date.
  - ii) Otherwise, assign ‘January.’
- 3) If the day is unknown, then:
  - i) If the month and year match the first dose date month and year, then impute the day of the first dose date.
  - ii) Otherwise, assign the first day of the month.

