7.5.5.10 Adverse Events

All AEs will be recorded from the time the subject signs the informed consent until 30 days after the last dose of study drug, or, if applicable, until the date the subjects signs the informed consent for the open-label extension study, UX001-CL302, whichever occurs sooner.

The determination, evaluation, reporting, and follow-up of AEs will be performed as outlined in Section 8.5. At each visit subjects will be asked about any new or ongoing AEs since the previous visit. Assessments of AEs will occur at each study visit.

Clinically significant changes from study baseline in interval history, physical and neurological examination findings, vital signs, weight, clinical laboratory parameters, and concomitant medications will be recorded as AEs or SAEs, if appropriate.

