#### 5.4 Patient Reported Outcomes

- **GNEM Functional Activities Scale (GNEM-FAS) Total Score** will be calculated as the sum of the Total Scores range from 0 to 100 with higher scores representing greater independence with functional activities. Subscale scores will be calculated for the Mobility, Upper Extremity and Self-Care domains. Mobility subscale scores range from 0 to 40 with higher scores representing greater mobility. Upper Extremity subscale scores range from 0 to 32 with higher scores representing more skilled, independent use of the arms during functional activity performance. Self-Care subscale scores range from 0 to 28 with higher scores representing greater independence with functional care activities.
- **Individual Neuromuscular Quality of Life Scale (INQoL) Subscale and QoL:** The individual domain scores will be calculated using the scoring algorithms outlined in Appendix 10.5 Derived Variables.
- **Number of doses administered** will be calculated for each subject by summing the number of doses administered over all visits.
- **Prior medications** include all medications taken by the subject from 30 days prior to the signing of the informed consent until the first dose of study medication is administered.
- **Concomitant medications** include all medications that are taken after the first dose of study medication is administered.

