**B. Stop Dates**

- 1) If the year is unknown, then the date will not be imputed and will be assigned a missing value.
- 2) If the month is unknown, then assign ‘December.’
- 3) If the day is unknown, then assign the last day of the month.

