## 8.9 Safety Analyses

Analysis of safety will be performed on the safety analysis set. Blinded study data will be monitored on an ongoing basis by the clinical study team including the medical monitor and the clinical drug safety team to ensure patients' safety.

Safety will be evaluated by the incidence, frequency and severity of AEs and SAEs, including clinically significant changes from study baseline to scheduled time points in:

- Interval history
- Vital signs and weight
- Physical examination findings
- Clinical laboratory evaluations
- Suicidal ideation and behavior assessments
- Concomitant medications

All AEs will be coded using the Medical Dictionary for Regulatory Activities (MedDRA 17.1 or beyond). The incidence and frequency of treatment emergent AEs (occurred after the first dose of study drug) will be summarized by System Organ Class (SOC), Preferred Term (PT), severity, and relationship to treatment. The numbers (frequency) and incidence rates of AEs and SAEs will be summarized by treatment group. A by-subject listing will be provided

for those subjects who experience a SAE, including death, or experience an AE associated with early withdrawal from the study or study drug treatment. Each of these outputs will include tabulation by maximum severity for each SOC and preferred term. Summaries of AEs will be provided in descending order of frequency by SOC and preferred term.

Additional tables summarizing patient incidence (by preferred term) of the following will be generated:

- All AEs;
- SAEs;
- Treatment-related AEs;
- Treatment-related SAEs;
- AEs leading to the discontinuation of study drug or discontinuation of study;
- Deaths.

Separate outputs maybe be provided for subgroups defined by gender, and race (if feasible). Detailed listings for all AEs and listings and/or narratives will be provided for serious and significant AEs, deaths (with “on-study” deaths [deaths that occur before the end of safety follow-up period] identified).

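### SAP 7.2 can set an adverse event's start date after its own recorded stop date, so an event that ended before dosing can be counted as treatment-emergent

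*SAP*

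**What the plan says.** SAP 7.2 sets out its scope: "The following conventions will be used to impute missing portions of dates for adverse events and concomitant medications".

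Under A. Start Dates there are two branches that use the first-dose date. Rule 3(i), for an unknown day, reads: "If the month and year match the first dose date month and year, then impute the day of the first dose date". Rule 2(i), for an unknown month, assigns the month and day of first dose when the year matches. If the known part does not match, the rules fall back to January or to the first of the month. For an unknown year, rule 1 says: "If the year is unknown, then the date will not be imputed and will be assigned a missing value". None of the start rules, and none of the rules under B. Stop Dates, compares one date with the other.

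The opening paragraph of 7.2 concedes that the imputed date may not always be the most conservative, and adds: "In those circumstances, the imputed value may be replaced by a date that will lead to a more conservative analysis".

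SAP 8.9 summarises "treatment emergent AEs (occurred after the first dose of study drug"). It gives no rule for an event whose onset falls on the first-dose date or is missing.

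Protocol 7.5.5.10 fixes the collection window: "All AEs will be recorded from the time the subject signs the informed consent until 30 days after the last dose". Protocol Table 2.1, footnote a, allows up to 28 days between screening and baseline, and Protocol 7.5.1.1 dates the Screening Visit by the signing of consent.

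**The concern.** The database will hold adverse events that began and ended before the first tablet. If such an event has a complete stop date but only a partial start date, and the known part of the start matches first dose, the rule moves the start to the day of first dose. The stop date already shows that the event was over by then, but the rule does not use it.

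Two things follow. The listing shows an event that starts after it ends. More importantly, a classification based on the imputed start can put a pre-treatment event into the treatment-emergent tables. Those tables are the main safety comparison. They are broken down by preferred term, and SAP 8.9.1 and Appendix 10.6 single out gastrointestinal and liver-related terms. In a trial of about 80 subjects one record can change a term's incidence visibly.

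**Working it through.** The plan states no figure on this point, so there is none to reproduce. The check applies the rules literally.

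**1. The basic case.** First dose 20 June. Event recorded as starting in June of that year with the day unknown, stopped 10 June. Month and year match first dose, so rule 3(i) gives a start of 20 June. Start minus stop = 20 − 10 = 10 days, so the event starts ten days after it ended.

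**2. Each branch in turn.** Assumed first dose 15 March 2016:

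| Recorded start | Recorded stop | Rule | Imputed start | After the stop? |
|---|---|---|---|---|
| March 2016, day unknown | 10 March 2016 | 3(i) | 15 March 2016 | Yes |
| 2016, month unknown | 20 February 2016 | 2(i) | 15 March 2016 | Yes |
| February 2016, day unknown | 20 February 2016 | 3(ii) | 1 February 2016 | No |
| 2015, month unknown | 1 June 2015 | 2(ii) | 1 January 2015 | No |
| Year unknown | 1 May 2016 | 1 | Missing | Cannot be evaluated |

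Only the two first-dose branches fail. The fourth row tests the rule mechanically; an adverse event that early would precede consent.

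**3. How far the fault reaches.** The rules were run over an assumed grid: every first-dose date in 2016 (366), every onset from 28 days before to 366 days after first dose (395), and event lengths of 0, 3, 7 and 14 days, with stop dates fully recorded and all cells equally weighted.

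- Total: 366 × 395 × 4 = 578,280 events.
- Events that ended before first dose: for the four lengths there are 28 + 25 + 21 + 14 = 88 such onsets per first-dose date, and 88 × 366 = 32,208.
- Day unknown: start after stop in 14,388 events. That is 14,388 / 32,208 = 45% of those that ended before dosing, and 14,388 / 578,280 = 2.5% of all.
- Month unknown: start after stop in 30,723 events. That is 30,723 / 32,208 = 95% of those that ended before dosing, and 30,723 / 578,280 = 5.3% of all.
- Events that ended on or after first dose: 0 failures in both runs.

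These rates apply only if the start date is partial, and they rest on the uniform grid. They show where the fault lies, not how often it will occur.

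**4. From wrong date to wrong category.** The imputed start equals the first-dose date. SAP 8.9 asks whether the event came after first dose. If the first-dose day is counted as after, the pre-treatment event becomes treatment-emergent. If it is not, that event stays out, but so does every genuine on-treatment event whose partial start was imputed to the same day. The SAP does not choose, so the result depends on the programmer.

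**5. Size per record.** With about 80 subjects randomised 1:1, an arm holds about 40. One subject wrongly counted moves that arm's incidence for a term by 1 / 40 = 2.5 percentage points, provided the subject has no other qualifying event of that term.

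**6. With a cap.** Start = the earlier of the imputed start and the recorded stop. The basic case gives 10 June, and the first row of the table gives 10 March 2016. Both precede first dose, so neither event is treatment-emergent. The cap does nothing for the unknown-year row, which needs its own sentence.

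**The case against.** The strongest reply is that this will hardly ever matter. Baseline follows screening by 7 to 28 days (Protocol 7.5.1.2). Events are asked about at each visit and must be documented promptly (Protocol 7.5.5.10 and 8.5.4.1), and missing data are to be resolved with the investigator (Protocol 8.4.2). The same rule applies in both blinded arms and a pre-dose event cannot be caused by treatment, so no bias between arms is shown. Any over-count errs towards more treatment-emergent events, and 7.2 allows an imputed date to be replaced.

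Most of that stands, and it limits the size of the point. The override does not remove it. It is optional, has no trigger, and aims at a more conservative analysis rather than a possible date order. Counting a pre-dose event as treatment-emergent can itself be called conservative, so the clause gives no reason to correct it.

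Three stronger readings are tempting, and the documents do not support them:

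- **Medications.** A reader might infer that a drug stopped before first dose becomes concomitant once its start is imputed to the first-dose date. SAP 5.4 says: "Concomitant medications include all medications that are taken after the first dose of study medication is administered". A drug with a recorded stop before first dose does not meet that definition, whatever its imputed start.
- **Events with no start year.** A reader might infer that they drop out of the treatment-emergent tables. Rule 1 leaves the start missing, and 8.9 does not say how such events are classified. Their status is undefined, not excluded, and 8.9 still plans listings of all adverse events.
- **Stop dates.** An unknown stop month becomes December, which can fall after last contact. SAP 8.9 plans no analysis of event duration, so this affects listings only.

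**Conclusion.** The point holds in a narrow form. Rules 2(i) and 3(i) of SAP 7.2 can place an adverse event's start after its recorded stop, and such an event can be counted as treatment-emergent although it ended before dosing. The fault is confined to records with a partial start, a known part that matches first dose, and a stop before first dose.

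A reader might go on to conclude that the safety counts are misclassified. The documents support only that they can be. They give no frequency of partial dates, and the short pre-dose window and the repeated questioning about events suggest few. The step of 2.5 percentage points per subject assumes 40 per arm and no other event of the same term in that subject.

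No efficacy, power or alpha figure changes. This is a minor correction, worth making because a stated rule gives an impossible result and the remedy is almost free.

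**What to change.** Add to SAP 7.2:

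- An imputed start date is never later than the recorded stop date.
- An adverse event whose stop date is before first dose is not treatment-emergent.

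In the same edit, add to SAP 8.9:

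- An adverse event whose start is imputed to the first-dose date counts as treatment-emergent, unless its stop date is before first dose.
- An adverse event with a missing start date counts as treatment-emergent, unless its stop date is before first dose.

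A limit on imputed stop dates at last contact or death is optional, since it would tidy the listings only.

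The cost is a few lines of text and the matching programming. A small number of records may change category. No data collection or efficacy analysis is affected.
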